15.2.1.5. Montgomeri-Asberg Depression Rating Scale (MADRS)

The following measures based on the MADRS are designated as secondary efficacy variables:

- Change from baseline in the MADRS total score at each scheduled assessment (Weeks 1-6). Analysis will be analyzed using the MMRM method as specified for the primary endpoint analysis.
- Proportion of patients who achieve a treatment response, defined as $\geq 50\%$ reduction from baseline MADRS total score at Week 6 (LOCF) endpoint. The MADRS total score percentage change will be defined as $(\text{value at post-baseline visit} - \text{baseline value}) \times 100 / (\text{baseline value})$.
- Proportion of patients who achieve remission, defined as a MADRS total score of ≤ 12 at Week 6 (LOCF) endpoint.

15.2.2. MISSING DATA METHODS FOR SECONDARY EFFICACY VARIABLE(S)

Missing question data for questionnaires is accounted for in the variable descriptions. The methods used for analysis of these endpoints will address visit data that is missing.

Document: K:\DSP\SM-13496\KVA95374\Biostatistics\Documentation\SAP
Author: [REDACTED] Version Number: 1.0
Version Date: 30MAR2017

Template No: CS_TP_BS016 – Revision 3
Effective Date: 01May2012

Reference: CS_WI_BS005

Copyright © 2012 [REDACTED]. All rights reserved. [REDACTED]
The contents of this document are confidential and proprietary to [REDACTED]. Unauthorized use, disclosure or reproduction is strictly prohibited.

15.2.3. ANALYSIS OF SECONDARY EFFICACY VARIABLES

15.2.3.1. Analysis of CGI-BP-S and YMRS

The change from baseline in CGI-BP-S depression score and YMRS total score will be evaluated using an MMRM model, utilizing the same procedures and reporting as indicated for the MADRS primary efficacy MMRM analysis.

Additionally, the LOCF ANCOVA sensitivity analysis performed for the primary endpoint will also be performed for both scores.

These analyses will be conducted on both the ITT population. The analysis for CGI-BP-S will be repeated on the PP population.

15.2.3.2. Analysis of SDS and HAM-A

The change from baseline in SDS total score and HAM-A total score will be evaluated using the same LOCF ANCOVA method that is used for the sensitivity analysis of the primary efficacy variable.

Additionally, an analysis of days lost and days underproductive will be conducted from the SDS scale. This will take the form of a categorical summary supported by a logistic regression comparison versus placebo.

15.2.3.3. Analysis of Proportion of patients achieving a treatment response

Patients having a 50% or greater improvement from baseline in MADRS total score will be defined as "responders". Patients having a negative percentage change indicate improvement in MADRS total score. The proportion will be evaluated using logistic regression. The responder indicator will be set to 1 if the percentage improvement is greater than or equal to 50%, set to 0 if less than 50%, or set to missing if the percentage is missing. The responder variable will be modeled using treatment and pooled study center as a categorical factor, and baseline MADRS total score as a covariate. If the model fails to converge, the model will be attempted with country (in place of pooled center) and baseline MADRS total score. If the model still does not converge then geographic region will be used (in place of country). Contrasts will be evaluated for each SM-13496 treatment group compared to placebo. Odds Ratios, 95% CIs and Wald chi-square p-values will be presented for each contrast. Only n and percent will be presented in cases where the number of patients meeting the above composite variable criteria is too small for an analysis to be performed.

A Cochran-Armitage trend test will also be conducted on this outcome across placebo and the two SM-13496 treatment groups. In addition, the number needed to treat (NNT) to attain an additional responder will be derived for each SM-13496 dose group as follows:

$$\text{NNT} = 1 / \text{Risk Reduction}$$

where Risk Reduction (RR) = (SM-13496 response rate – placebo response rate). NNT results will be provided in whole numbers with any fractional values rounded up to the nearest whole number. The 95% CIs will also be presented and are computed by taking the reciprocal of the 95% lower and upper bounds of the RR. The lower confidence limit will be rounded down to the largest integer value that is less than the computed estimate, and the upper confidence limit will be rounded up to the smallest integer value that is greater than the computed estimate.

Between-group effect size represented by Cohen's h will also be presented and will be derived as follows:

$$h = 2 \times \arcsin(\sqrt{\text{SM-13496 response rate}}) - 2 \times \arcsin(\sqrt{\text{placebo response rate}})$$

Document:	K:\DSP\SM-13496\KVA95374\Biostatistics\Documentation\SAP	Version Number:	1.0
Author:	[REDACTED]	Version Date:	30MAR2017

Template No: CS_TP_BS016 – Revision 3
Effective Date: 01May2012

Reference: CS_WI_BS005

Copyright © 2012 [REDACTED] All rights reserved.
The contents of this document are confidential and proprietary to [REDACTED]. Unauthorized use, disclosure or reproduction is strictly prohibited.

This analysis will be performed for the ITT population, and will be repeated by country. Similar responder classifications are defined for subjects with 20%, 30%, and 40% or greater improvement from baseline in MADRS total score. Subjects classified as 20%, 30% and 40% responders will be analyzed as in the previous paragraph, with the exception of the Cochran-Armitage test which is exclusive to the 50% analysis.

This analysis will be repeated for a subgroup of patients who also achieved response criteria on the CGI-BP-S scale. This is classed as a CGI-BP-S score ≤ 3 .

The time to response of MADRS will be analyzed using a time-to-event analysis. Patients failing to achieve a response during the study period will be censored at the day of completion/discontinuation from the study. Kaplan-Meier results will be displayed for the 25%, 50% and 75% quartiles. Additionally, the Kaplan-Meier estimates of the response rate for each treatment group will be displayed. A log-rank test will also be used to compare SM-13496 with placebo, and also compare the two SM-13496 doses. A Kaplan-Meier figure will also be produced to support the analysis.

The time-to-event analysis will also use a Cox proportional hazards model with fixed effects for treatment, geographic region and baseline MADRS total score as a continuous covariate. This model will be used to generate hazard ratios for the same comparisons as specified for the log-rank test.

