7.5. EXAMINATION OF SUBGROUPS

Subgroup analyses will be conducted on change from baseline results for MADRS total score and CGI-BP-S depression score from Week 1 to Week 6, including Week 6 (LOCF) endpoint. It should be noted that the study was not designed to detect treatment differences with high statistical power within subgroups.

The efficacy analyses to be repeated on subgroups are the MMRM and ANCOVA methods for both MADRS and CGI-BP-S. This analysis will only be performed on the ITT population. Additionally, SDS, HAM-A and YMRS will be analyzed separately by country.

A subgroup analysis will also be performed upon a selection of safety parameters. These parameters are DIEPSS

Document:	K:\DSP\SM-13496\KVA95374\Biostatistics\Documentation\SAP		
Author:	[REDACTED]	Version Number:	1.0
		Version Date:	30MAR2017

Template No: CS_TP_BS016 -- Revision 3

Reference: CS_WI_BS005

Effective Date: 01May2012

Copyright © 2012 [REDACTED] All rights reserved.

The contents of this document are confidential and proprietary to [REDACTED]. Unauthorized use, disclosure or reproduction is strictly prohibited.

(ANCOVA only) as well as weight, BMI, QTc, and selected laboratory parameters (ANCOVA only). A small number of specified Adverse Event tables will also be split by subgroup. Safety parameter subgroup analyses will be performed on the Safety population.

The full analysis methods for subgroups are detailed in section 15.2.4.

The following subgroups will be assessed and described within the exploratory analysis sections:

- Sex:
 - Male
 - Female
- Age (years):
 - <55
 - ≥55
 - And
 - <65
 - ≥65
- Bipolar I Diagnosis Subtype (Efficacy Analyses only)
 - Rapid Cycling
 - Non-rapid Cycling
- Country
 - Japan
 - Ukraine
 - Philippines
 - Taiwan
 - Russia
 - Malaysia
 - Lithuania
 - Slovakia

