15.2.1. SECONDARY EFFICACY VARIABLES & DERIVATIONS

15.2.1.1. Clinical Global Impressions Scale – Bipolar Version - Severity of Illness (CGI-BP-S)

The change from baseline in CGI-BP-S depression score at Week 6 is a secondary efficacy variable. The CGI-BP-S depression score, measured at Screening, Baseline, Weeks 1 to 5, and Week 6/Early Term, is a single value, clinician-rated assessment of the subject's current severity of depression and ranges from 1= 'Normal, not ill' to 7= 'Very severely ill'.

The change from baseline will be calculated as the score at Week 6 – score at baseline.

A LOCF endpoint will also be derived for CGI-BP-S. For calculation details, please see section 6.3.

Additional efficacy ANCOVA analyses will be conducted based on change from baseline in CGI-BP-S depression score at Weeks 1 – 6, and Week 6 LOCF endpoint.

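### Read literally, the SAP repeats the MADRS responder analysis only in patients with a post-randomisation CGI-BP-S score of 3 or less; a composite responder in all ITT patients should be defined instead

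*SAP*

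**What the plan says.** SAP 15.2.3.3 sets out the responder analysis: "Patients having a 50% or greater improvement from baseline in MADRS total score will be defined as" responders. The flag goes into a logistic regression giving odds ratios, with a number needed to treat (NNT) and Cohen's h. Its population is clear: "This analysis will be performed for the ITT population, and will be repeated by country". The section then re-runs the analysis at 20%, 30% and 40% improvement, and next states: "This analysis will be repeated for a subgroup of patients who also achieved response criteria on the CGI-BP-S scale". The criterion follows: "This is classed as a CGI-BP-S score" of 3 or less.

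SAP 15.2.1.1 says the CGI-BP-S depression score is "measured at Screening, Baseline, Weeks 1 to 5, and Week 6/Early Term". It also makes that score an efficacy outcome: "The change from baseline in CGI-BP-S depression score at Week 6 is a secondary efficacy variable".

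SAP 7.5 introduces its subgroup list with "The following subgroups will be assessed and described within the exploratory analysis sections". The list holds sex, age, bipolar I subtype and country. All are baseline factors, and CGI-BP-S response is not among them. Protocol 9.5.3 does not contain the CGI-BP-S repeat, so it supplies no definition to fall back on.

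**The concern.** A subgroup defined by a baseline factor keeps the randomised comparison within it. A subgroup defined by an outcome that treatment can change does not. If lurasidone moves more patients to a CGI-BP-S score of 3 or less than placebo does, the two sets of patients reaching that score are different selected fractions of their arms. An odds ratio, NNT or Cohen's h calculated among them then mixes the treatment effect with the selection.

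A programmer following the sentence as it stands could filter the dataset on CGI-BP-S and run the model on what remains. The output would carry odds ratios, confidence intervals and p-values that look like those of the ITT analysis and could be quoted beside them, although they would not estimate a treatment effect in any randomised group.

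**Working it through.** **1. What the sentence can mean.**

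- *Restrict to CGI-BP-S of 3 or less, then model MADRS response.* This conditions on a post-randomisation outcome.
- *Restrict to patients meeting both criteria.* Every member then has responder flag 1. The outcome does not vary and no logistic model can be fitted.
- *Redefine the responder as meeting both criteria, with all ITT patients in the denominator.* This is a sound analysis, but the section does not define the flag or the denominator.

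Two further items are open under every reading. The subscale is not named, although the scale has depression, mania and overall parts (protocol 3.4.1.2). The time point for the criterion is not given either.

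**2. Illustration of the first reading.** The plan gives no response rates, so there is no figure of its own to reproduce. Assumptions: MADRS response *m* is 50% on drug and 36% on placebo (ITT difference 14 points); the placebo rate of CGI-BP-S of 3 or less is 42%; the latent correlation *r* is 0.6 to 0.8. The drug rate of CGI-BP-S of 3 or less, *c*, is varied.

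Joint rate: J = Φ₂(Φ⁻¹(m), Φ⁻¹(c); r). Response rate within the subgroup: J / c. Composite rate in all ITT patients: J.

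Example with c = 55% versus 42% and r = 0.8:
- Drug: J = 0.4209, and 0.4209 / 0.55 = 76.5%.
- Placebo: J = 0.2889, and 0.2889 / 0.42 = 68.8%.
- Subgroup difference: 7.8 points from unrounded values. Composite difference: 0.4209 − 0.2889 = 13.2 points.

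| CGI-BP-S ≤ 3, drug vs placebo | Subgroup difference (points) | Composite difference (points) |
|---|---|---|
| 60% vs 42% | 4.7–7.7 | 15.2 |
| 55% vs 42% | 7.8–9.7 | 13.0–13.2 |
| 45% vs 42% | 13.7–13.8 | 8.0–8.2 |
| 42% vs 42% | 15.1–15.4 | about 6.4 |

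The last column is a different estimand. The gap between the two columns does not measure bias.

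**3. No effect on MADRS, an effect on CGI-BP-S.** Set m = 36% in both arms and keep c = 55% versus 42%. At r = 0.6 the subgroup rates are 52.8% and 58.7%, so OR = (0.528/0.472) / (0.587/0.413) = 0.79. At r = 0.8 they are 59.5% and 68.8%, so OR = (0.595/0.405) / (0.688/0.312) = 0.67. The ITT odds ratio is 1.00 in both cases.

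**4. Second illustration, using protocol 3.5.** From the protocol: SD 10, effect size 0.35, and placebo mean change −9.5 (from the earlier US monotherapy study). Assumed: mean baseline MADRS 28 or 32 with SD 5 and values held within 20 to 60; correlation of MADRS change with CGI-BP-S 0.6 to 0.9; half of placebo patients at CGI-BP-S of 3 or less. Simulated with 2,000,000 patients per arm.

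- MADRS effect 0.35: ITT OR 1.73–1.75.
- Subgroup OR: 1.61–1.73 if the CGI-BP-S effect is 0.2; 1.37–1.48 if 0.35; 1.14–1.36 if 0.5.
- No MADRS effect, CGI-BP-S effect 0.35: ITT OR 1.00, subgroup OR 0.64–0.81.

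**The case against.** The strongest reply is that a composite was meant. The word *also* in the sentence points to MADRS responders who additionally meet the CGI-BP-S criterion. The same section uses composite wording in its small-numbers rule: "Only n and percent will be presented in cases where the number of patients meeting the above composite variable criteria is too small". The sentence follows the 20%, 30% and 40% re-runs, so one more responder classification fits the sequence. CGI-BP-S response is absent from the SAP's own subgroup list. This reading is plausible, and it limits how firmly the literal one can be asserted. It does not settle the matter: the composite wording recurs in SAP 16.7.5 for treatment-emergent mania and may be carried-over text, and the output templates mentioned in SAP 8, which might decide it, are not available here. Even if a composite was intended, the section leaves it undefined.

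The second reply is that the size is assumed, and this stands. A reader might infer that the subgroup analysis is biased toward a smaller drug–placebo difference. The documents do not support that in general: they give no CGI-BP-S response rates, and the table runs from well below the 14-point ITT difference to slightly above it.

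The third reply is that little depends on this analysis. That also stands. The Hochberg family in SAP 7.4 covers only the two primary comparisons. MADRS response keeps its own ITT analysis, and CGI-BP-S depression is analysed separately by MMRM in ITT (SAP 15.2.3.1).

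**Conclusion.** The point holds as a defect of specification in one supportive analysis. Taken literally, the rule gives either a comparison that is no longer randomised whenever treatment affects CGI-BP-S, or a subgroup made up only of responders. The reading that would work is not written down.

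No single figure for the distortion can be given. Under the stated assumptions the subgroup difference ranges from 4.7 to 15.4 points against an ITT difference of 14, depending on the CGI-BP-S effect. With an effect on CGI-BP-S but none on MADRS, the subgroup can show a false odds ratio below 1.

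A reader might go further and infer that the plan breaks randomisation for the trial's efficacy conclusions. It does not. The primary MMRM, its multiplicity control, the sample size and the main ITT responder analysis are unaffected.

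**What to change.** Replace the sentence in SAP 15.2.3.3, and the criterion that follows it, with:

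> A composite responder (MADRS reduction of at least 50% and CGI-BP-S depression score of 3 or less, both at Week 6 LOCF) will be set to 1 if both are met, 0 if either is not met, and missing only if it cannot be determined because a component is missing. It will be analysed in all ITT patients with the same logistic model, NNT and Cohen's h, without the Cochran-Armitage test.

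This fixes the denominator, subscale and time point. Its missing-data rule follows the section's existing practice of leaving the responder flag missing when its input is missing, rather than counting an absent CGI-BP-S score as non-response. The cost is small: one extra derived flag and an explicit rule for a missing CGI-BP-S score.

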15.2.3.4. Analysis of Proportion of patients achieving a treatment remission

Patients with a MADRS total score ≤ 12 are classed as being in remission. The proportion of patients achieving a remission will be analyzed using the same methods as for the number of patients achieving a response, with the exception of the Cochran Armitage Test.

In summarizing the number of subjects achieving remission, the number of subjects achieving a MADRS total score ≤ 8 and ≤ 10 will also be presented.

15.2.4. SUBGROUP ANALYSIS METHODS

Subgroup analysis will be performed for the change from baseline in the MADRS total score and the CGI-BP-S (depression) score at Week 6. For details of the subgroups, please refer to section 7.5.

For all subgroups other than country, inferential analysis of treatment-by-subgroup interaction at Week 6 will be performed using the MMRM method on the ITT population. The model will include treatment, visit, baseline data, pooled study site, subgroup, treatment-by-subgroup, treatment-by-visit, visit-by-subgroup, and treatment-by-subgroup-by-visit interactions.

Analysis for country will be conducted using the MMRM method described above for the primary efficacy variable on the ITT population. The analysis will be repeated for each country using a separate model to create estimates in each case.

Safety parameters will be evaluated using a non-parametric rank ANCOVA test at week 6. This will use the same model logic as specified for the analyses using MMRM. Country will be evaluated separately, while other subgroups will be modeled with interaction terms included.

16. SAFETY OUTCOMES

All outputs for safety outcomes will be based on the Safety Population.

Document:	K:\DSP\SM-13496\KVA95374\Biostatistics\Documentation\SAP		
Author:	[REDACTED]	Version Number:	1.0
		Version Date:	30MAR2017

Template No: CS_TP_BS016 – Revision 3
Effective Date: 01May2012

Reference: CS_WI_BS005

Copyright © 2012 [REDACTED] All rights reserved.
The contents of this document are confidential and proprietary to [REDACTED]. Unauthorized use, disclosure or reproduction is strictly prohibited.

16.1.2. TEAEs LEADING TO DISCONTINUATION OF STUDY MEDICATION

TEAEs leading to permanent discontinuation of study medication will be identified by using the 'action taken' variable collected on the eCRF.

For TEAEs leading to discontinuation of study medication, summaries of incidence rates (frequencies and percentages) by SOC and PT will be prepared.

16.1.3. SERIOUS ADVERSE EVENTS

Serious adverse events (SAEs) are those events recorded as "Serious" on the Adverse Events page of the eCRF. A summary of serious TEAEs by SOC and PT will be prepared. A listing will provide details of SAEs and indicate any drug relationship.

16.1.4. ADVERSE EVENTS LEADING TO DEATH

TEAEs leading to Death are those events which are recorded as "Fatal" on the Adverse Events page of the eCRF. These events will be listed.

16.1.5. ADVERSE EVENTS OF SPECIAL INTEREST

16.1.5.1. TEAEs relating to Extrapyramidal Symptoms

TEAEs relating to Extrapyramidal symptoms will be summarized by Preferred Term. These will be identified by using a list of specified terms from medical personnel. This summary will be repeated separated by country.

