3.4.3 Safety variables

- Incidence of Adverse events (AEs) and Adverse drug reactions (ADRs)
- Incidence of extrapyramidal AEs and ADRs
- Proportion of patients with concomitant use of antiparkinson medication.
- Change from baseline in the DIEPSS total score (except for the overall severity score) at the final assessment
- Change from baseline in the individual DIEPSS symptoms scores at the final assessment
- Change from baseline in the serum prolactin concentration at the final measurement
- Change from baseline in ECG parameter (QTc) at the final measurement

- Change from baseline in fasting blood glucose, HbA1c (NGSP), glycoalbumine, total cholesterol, LDL cholesterol, HDL cholesterol, and triglycerides at the final measurement
- Change from baseline in body weight at the final measurement
- Laboratory measures and vital signs
- Proportion of patients with a YMRS total score of ≥ 16 at 2 or more consecutive assessments or with any adverse events related to mania symptoms
- Proportion of patients with any instance of suicide attempt or suicidal ideation based on the Columbia-Suicide Severity Rating Scale (C-SSRS).

Rationale

Extrapyramidal symptoms are the most common side effects associated with antipsychotics and usually treated with antiparkinson drugs. The DIEPSS¹⁸⁾ is an evaluation scale for the extrapyramidal symptoms. Antipsychotics are known to increase serum prolactin concentration¹⁹⁾. Some atypical antipsychotics are known to influence glucose metabolism, lipid metabolism, and body weight. Some drugs affect cardiac rhythm (eg, QT interval prolongation).

Switching from a depressive phase into a manic phase (manic switching) in bipolar disorder is an important concern with antidepressants and antipsychotics. The YMRS total score and incidence of adverse events related to manic symptoms will be used for assessing the risk of manic switching. The rate of suicide is high for bipolar disorder, and prevention of suicide is one of the important aspects in the treatment of bipolar disorder. The C-SSRS²⁰⁾ is a tool designed to systematically assess and track suicidal adverse events (suicidal attempts and suicidal ideation), and is able to comprehensively identify suicidal events while limiting the over-identification of suicidal behavior.

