5.3.2 Restricted concomitant medications/therapies

5.3.2.1 Psychotropic medications

(1) Psychotropic medications (excluding antiparkinson drugs, anxiolytics, and hypnotics)

Psychotropic medications (eg, antipsychotics, antidepressants, mood stabilizers) excluding permitted antiparkinson drugs, anxiolytics, and hypnotics (see Items (2) to (4) in this section) will be restricted as follows:

- For patients untreated with psychotropic medication at screening, psychotropic medications will be prohibited from screening until the end of the treatment phase.
- For patients treated with any psychotropic medications at screening, the psychotropic medications should be titrated down appropriately and terminated at least 3 days before the initiation of the study treatment. Psychotropic medications will be prohibited during the treatment phase.

(2) Medications for extrapyramidal symptoms (eg, antiparkinson drugs)

Medications for extrapyramidal symptoms (eg, antiparkinson drugs) will be restricted as follows:

- For patients untreated with drugs for extrapyramidal symptoms at screening, drugs for extrapyramidal symptoms will be prohibited from screening until the initiation of the study treatment.
- For patients treated with drugs for extrapyramidal symptoms at screening, the drugs should be titrated down appropriately and terminated before the initiation of the study treatment.
- For all patients, if any extrapyramidal symptoms develop or worsen after the initiation of the study treatment, only one of the drugs listed in Table 4 may be used, within the dose range specified in the table. If the drug is not effective, the drug may be replaced by another drug among the drugs listed in Table 4. For akathisia, propranolol (≤ 120 mg/day), amantadine (≤ 300 mg/day), or one of the drugs listed in Table 4 may be used. If the above-mentioned drugs are not available at the study site, similar drugs at equivalent doses may be used with prior authorization of the medical monitor.
- For all patients, antiparkinson drugs and other drugs for extrapyramidal symptoms will be prohibited for prophylactic purposes.

Table 4 Permitted concomitant antiparkinson drugs

Drug	Daily dose
Biperiden	≤ 16 mg
Trihexyphenidyl	≤ 10 mg
Benztropine	≤ 6 mg
Diphenhydramine	≤ 300 mg

(3) Anxiolytics

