6.4.5 Drug-Induced Extrapyrarnidal Symptom Scale (DIEPSS)

The DIEPSS¹⁸⁾ is a clinician-rated assessment of extrapyramidal symptom induced by antipsychotics and consists of eight individual parameters; gait, bradykinesia, sialorrhea, muscle rigidity, tremor, akathisia, dystonia, and dyskinesia; and one global assessment; overall severity. The severity of each item is graded 0 (normal) to 4 (severe). The investigator will assess the DIEPSS at Visits 2 to 8 and at discontinuation. The assessment at Visit 8 or at discontinuation should be performed within 72 hours after the final administration of the study drug and before the initiation of post treatment with antipsychotics or the study drug in the long-term study.

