3.3. CHANGES TO ANALYSIS FROM PROTOCOL

There were no changes made to the statistical analysis as planned in the final study protocol.

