16.7. OTHER SAFETY ASSESSMENTS

16.7.1. DRUG-INDUCED EXTRAPYRAMIDAL SYMPTOM SCALE (DIEPSS)

The DIEPSS is a clinician-rated assessment of extrapyramidal symptoms induced by antipsychotics and consists of eight individual parameters; gait, bradykinesia, sialorrhea, muscle rigidity, tremor, akathisia, dystonia, and dyskinesia; and one global assessment; overall severity. The severity of each item is graded 0 (normal) to 4 (severe), and then a summation of all questions (excluding overall severity) provides the total score which is used for analysis. The investigator will assess the DIEPSS at Visits 2 to 8 and at discontinuation. The assessment at Visit 8 or at discontinuation should be performed within 72 hours after the final administration of the study drug and before the initiation of post treatment with antipsychotics or the study drug in the long-term study.

A LOCF endpoint will also be derived for DIEPSS. For calculation details, please see section 6.3.

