APPENDIX 4. MEDICAL REVIEW OF TERMS

EPS Terms	Metabolic Terms	Combined Terms	Treatment Emergent Mania Terms
Muscle rigidity	Blood cholesterol increased	Parkinsonism : Muscle rigidity, Bradykinesia, Parkinsonism, Tremor, Psychomotor retardation	Bipolar I disorder
Trismus	Blood glucose increased		Hypomania
Bradykinesia	Blood insulin increased		Mania
Dystonia	Blood triglycerides increased		
Parkinsonism	Fructosamine increased		
Tremor	Glucose urine present	Dystonia: Dystonia, Trismus	
Psychomotor retardation	High density lipoprotein decreased		
	Low density lipoprotein increased		
	Weight increased	Somnolence: Sedation , Somnolence	
	Glucose tolerance impaired		
	Dyslipidaemia		
	Hyperinsulinaemia		
	Hyperlipidaemia		

Document: K:\DSP\SM-13496\KVA95374\Biostatistics\Documentation\SAP
 Author: [REDACTED] Version Number: 1.0
 Version Date: 30MAR2017

Template No: CS_TP_BS016 – Revision 3
 Effective Date: 01May2012

Reference: CS_WI_BS005

Copyright © 2012 [REDACTED] All rights reserved. [REDACTED] Unauthorized use, disclosure or reproduction is strictly prohibited.

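### The SAP's term list for extrapyramidal adverse events leaves out akathisia and dyskinesia, which both documents treat as extrapyramidal symptoms

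*SAP*

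**What the plan says.** The protocol names "Incidence of extrapyramidal AEs and ADRs" as a safety variable (3.4.3) and includes it in secondary objective 5. Protocol 9.7.1 asks for the number and percentage of patients with at least one event, and repeats that summary for extrapyramidal events. The protocol gives no list of qualifying terms and excludes none.

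SAP 16.1.5.1 turns this into a selection rule: "These will be identified by using a list of specified terms from medical personnel". The summary is by preferred term and is repeated by country. The section cites no appendix, but Appendix 4 is a medical review of terms with a column headed EPS Terms, and the SAP contains no other such list. That column has seven entries. The Combined Terms column beside it groups the same seven as "Parkinsonism : Muscle rigidity, Bradykinesia, Parkinsonism, Tremor, Psychomotor retardation" and "Dystonia: Dystonia, Trismus".

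Elsewhere both documents describe extrapyramidal symptoms more widely. SAP 16.7.1 calls the DIEPSS an "assessment of extrapyramidal symptoms induced by antipsychotics and consists of eight individual parameters; gait, bradykinesia, sialorrhea, muscle rigidity, tremor, akathisia, dystonia, and dyskinesia". Protocol 6.4.5 gives the same eight items: "gait, bradykinesia, sialorrhea, muscle rigidity, tremor, akathisia, dystonia, and dyskinesia". Protocol 5.3.2.1, item (2), on medications for extrapyramidal symptoms, has a sentence that begins "For akathisia, propranolol". SAP 3.3 declares: "There were no changes made to the statistical analysis as planned in the final study protocol".

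**The concern.** The list decides who counts as having an extrapyramidal adverse event, and it is narrower than the trial's own account of these symptoms. A patient could receive permitted treatment for akathisia under the protocol's extrapyramidal heading and have akathisia scored and analysed as a DIEPSS item, yet not count in the extrapyramidal event table.

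At stake is a descriptive safety figure that readers will take as the extrapyramidal rate of an antipsychotic. If akathisia or dyskinesia was reported without a listed term in the same patient, that figure is too low, overall and by country. The rule applies to every arm, so the effect on the difference from placebo cannot be told from the documents. Efficacy conclusions are not affected.

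**Working it through.** The plan states no figure to reproduce. The check is a comparison of lists, followed by an illustration of size.

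**Step 1: is the list complete as printed?** The Parkinsonism group in Appendix 4 has 5 terms and the Dystonia group has 2, and 5 + 2 = 7. These are exactly the seven entries of the EPS Terms column, so a term lost in reading the PDF is an unlikely explanation.

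**Step 2: compare the list with the DIEPSS items** (Protocol 6.4.5; SAP 16.7.1).

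| DIEPSS item | In EPS Terms column? |
|---|---|
| Bradykinesia | yes |
| Muscle rigidity | yes |
| Tremor | yes |
| Dystonia | yes |
| Akathisia | no |
| Dyskinesia | no |
| Gait | no |
| Sialorrhea | no |

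Four of the eight items have a matching term and four do not. Akathisia has a second source in Protocol 5.3.2.1. For dyskinesia the support is the scale itself, in both documents.

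**Step 3: look for a stated exclusion.** There is none in Protocol 3.4.3 or 9.7.1, in SAP 16.1.5.1, or in Appendix 4. SAP 3.3 reports no change from the protocol.

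**Step 4: illustrate the size.** The documents give no rate for either event, so the rates below are assumptions.

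- Patients: SAP Table B sums to 524. With 1:1:1 allocation (Protocol 4.2), active patients ≈ 524 × 2/3 ≈ 349.
- Japan: pooled centers 901 to 909 sum to 179, so active patients ≈ 179 × 2/3 ≈ 119.
- Formula: patients missed = active patients × r × s. Here r is the assumed proportion with akathisia or dyskinesia, and s is the assumed share of those with no listed term.

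| r | s = 50% | s = 100% |
|---|---|---|
| 0% | 0 | 0 |
| 2% | 349 × 0.02 × 0.5 ≈ 3 | 349 × 0.02 ≈ 7 |
| 10% | 349 × 0.10 × 0.5 ≈ 17 | 349 × 0.10 ≈ 35 |

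At r = 10% and s = 100%, the Japan table would miss 119 × 0.10 ≈ 12 active patients. Placebo patients would be missed by the same rule at whatever rate applies to them.

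**The case against.** The strongest reply is that Appendix 4 records a review of terms already reported and was never a prospective definition. Its title points that way. The SAP is dated 30MAR2017, after the last patient's last visit on 20FEB2017 (SAP 15.1.4.2), and the version history says that version 1.0 took in information from study data. If neither term occurred in the blinded data, no patient is miscounted and only an explanatory sentence is missing. This is plausible, but the SAP does not say it, so a reader cannot tell a term that was never reported from one that was excluded.

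Other points stand in part:

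- SAP 16.1.5.1 does not cite Appendix 4. True, but no other list exists to serve the rule.
- The Combined Terms column merges several preferred terms under one label, so a single term such as akathisia would need no group there. Granted. The 5 + 2 match shows only that the printed list is probably intact.
- The protocol lists no extrapyramidal event terms, so the SAP's statement of no change is weak evidence. Granted. The case rests on how both documents describe these symptoms.
- The DIEPSS is a severity scale, not a coding rule, and gait and sialorrhea also lack terms. This is a reason to leave those two domains to medical review. It does not explain the absence of akathisia and dyskinesia.
- Little information is lost. SAP 16.1.1 tabulates all treatment-emergent events by preferred term and repeats this by country, SAP 16.7.3.1 analyses each DIEPSS item, and no between-group test of extrapyramidal events is planned. This limits the harm to the grouped count.

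**Conclusion.** The concern holds. The term list is narrower than the documents' own description of extrapyramidal symptoms, with no reason given. Applied as written, it undercounts a protocol-named safety variable for any patient whose only such event is akathisia or dyskinesia.

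The omission from the text is certain; the undercount is conditional. It is zero if neither term was reported. Under the assumed rates it runs from 0 to 35 active patients, and 35 is the top of an assumed range, not a limit found in the documents. The direction between arms is not established. Because the events remain visible by preferred term and through the DIEPSS items, this is something that should be fixed, but it does not threaten the trial's main conclusions.

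**What to change.** Before unblinding:

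1. Add akathisia and dyskinesia to the EPS Terms column of Appendix 4, and cite the appendix in SAP 16.1.5.1.
2. If the column is meant to hold only terms reported in the blinded data, say so and state that neither akathisia nor dyskinesia was reported.
3. If a figure without akathisia is wanted, show it as a second, labelled row.
4. Ask the medical reviewers to confirm whether terms for the gait and sialorrhea domains belong in the list.

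The cost is an edit to one appendix table and a sentence of text. The reported extrapyramidal rate may turn out slightly less favourable. Making the change before unblinding also avoids any suggestion that terms were chosen with knowledge of treatment.
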